4.1.1.2 Treatment Period

The treatment period will begin at the first dose of M3814 which will be administered continuously in combination with avelumab for Part A and Part FE, and with avelumab and RT for Part B.

Part A and Part FE: M3814 will be administered BID continuously, in combination with avelumab Q2W starting on Day 1 until PD or unacceptable toxicity.

Part B: M3814 will be administered QD. Radiotherapy will be given at the dose of 3 Gy per day. M3814 and RT will both be given starting Day 1 for 5 days/week for 2 weeks. Avelumab will be administered Q2W starting on Day 1 until PD or unacceptable toxicity.

Part A and Part B:

Dose-limiting toxicity (DLT) Assessment Period: will last 3 weeks in Part A and 4 weeks in
Part B (after the first administration of study intervention) for the evaluation of acute systemic
and local toxicity in all participants. The DLT assessment period in Part B will be longer than
for Part A because toxicities related to radiation including Radiation-Induced Lung Toxicities
(RILT) might occur within a few weeks to months after radiation. Therefore, additional RT
Safety Follow-ups are scheduled at 1, 3, and 12 months after the end of RT to investigate these
potential late toxicities.

Part FE:

 FE Assessment Period: will last 3 weeks (after the first administration of study intervention) for the evaluation of the effect of food conditions (fasted/fed) on M3814 PK.

Part A, Part B, and Part FE:

Participants who have experienced a confirmed complete response (CR) should be treated for a
minimum of 12 months with avelumab + M3814 in Part A and Part FE or avelumab in Part B
based on clinical judgment of benefit and/or until disease progression, unacceptable toxicity,
after confirmation of response as specified in the protocol. Where a participant with a confirmed
CR relapses after stopping treatment, during Long-term Follow-up, but prior to the
End-of-Trial, 1 reinitiation of treatment is allowed at the discretion of the Investigator and

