The primary endpoints of occurrence of DLTs as well as the secondary endpoint of occurrence, severity and duration of treatment-emergent adverse events (TEAEs) and treatment-related AEs according to National Cancer Institute-Common Terminology Criteria for Adverse Events (NCI-CTCAE) v 5.0 are standard objective measures of safety. A 3-week (Part A) and 4-week (Part B) period has been defined as the DLT assessment period to monitor DLT over 42 doses of M3814 and 2 administrations of avelumab for Part A and 10 administrations of M3814 and 8 fractions of RT (3 Gy each) and 3 administrations of avelumab for Part B. Secondary endpoints relating to PK, immunogenicity, and confirmed objective response as assessed by the Investigator using RECIST v1.1 criteria are also standard measurements. Duration of response, PFS and OS will also be determined as secondary endpoints and will serve to assess whether the objective response is associated with lasting clinical and survival benefit.

Part FE:

The primary endpoint is to evaluate the FE (fasted/fed state) on PK of M3814. A 3-week period has been defined as the FE Assessment Period to monitor the exposure both after single and repeated administration of M3814 over 42 doses of M3814 and 2 administrations of avelumab. Secondary endpoints relating to the effects of prandial state on the safety profile of M3814 along with immunogenicity and confirmed objective response as assessed by the Investigator using RECIST v 1.1 criteria are also standard measurements. Duration of response, PFS, and OS will

also be determined as secondary endpoints and will serve to assess whether the objective response is associated with lasting clinical and survival benefit.

Part A, Part B, and Part FE:

The exploratory pharmacodynamic assessments were selected based on the known mechanism of action and effects of M3814 and are relevant to the response, safety, or resistance to the combination. These assessments will contribute to the understanding of AEs and help in the determination of the RP2D.

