6.6.2 Dose Selection (Part FE)

The starting dose of M3814 would be 200 mg total daily dose given as 100 mg BID. Subsequent doses and schedules will be determined based on the PK and safety data generated in previous

cohorts of Part A and Part FE and should be within the dose ranges already declared safe and tolerable in Part A. Avelumab will be administered Q2W as an IV infusion over 1 hour, starting on Day 1, at a fixed dose of 800 mg in all dose levels. Guidance on premedication is given in Section 6.5.5.

The FE Assessment Period is considered completed and a participant evaluable for subsequent dose level decisions, when the PK and minimum safety evaluations have been performed (hematology, chemistry, and clinical assessments), and the participant has received:

 at least 80% of the planned doses of M3814 (i.e., 34 of 42 doses with BID dosing regimen) and 100% of the planned avelumab doses (2 administrations) during the FE Assessment Period of 3 weeks.

The results from Part FE will be reviewed and evaluated by the Sponsor and if deemed necessary by the SMC to determine a potential impact on the study dosing recommendations for M3814 and/or safety profile of M3814 when given in combination with avelumab.

Cohorts of at least 3 participants each will be treated at the same dose level of M3814 (starting dose: 100 mg tablet formulation, BID) in combination with avelumab. On the day of avelumab administration, M3814 can be given prior to the start or just after the end of avelumab infusion. A preselected set of acceptable doses as described in Table 12, will be considered once declared as safe and tolerable in Part A, however, doses which are not part of the prespecified set may be chosen as well, as long as they are within the prespecified dose ranges based on considerations of PK and safety data generated in previous cohorts. If the sample size in Part FE has to be increased to accommodate additional dose levels, a protocol amendment with rationale will be submitted prior to implementation. The Sponsor and/or the SMC may decide to continue or stop the assessment of FE in subsequent dose level (s). This decision will be based on PK and safety data generated in the previous cohorts in Part A and/or Part FE and/or emerging data from the clinical studies which are currently evaluating the human pharmacology, safety, and tolerability of M3814. It is anticipated that 6 to 12 participants (3 to 6 participants at each dose level) may be needed.

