6.6.5.3 Part FE

M3814: A 50 mg tablet for oral administration is used during the treatment phase. The starting dose will be 100 mg BID. Subsequent doses and schedules will be determined based on PK and safety data.

For M3814 administrations, participants will be instructed as follows:

On Day 1 and Day 22, participants will be instructed to fast overnight for at least 8 hours followed by the meal provided at the site. M3814 should be administered within 30 minutes after the meal. The drug should be taken with approximately 240 mL (8 fluid ounces) of water. Additional water is allowed ad libitum except for 1 hour before and 1 hour after M3814 administration.

On Day 15, participants will be instructed to fast overnight for at least 8 hours followed by the M3814 administration at the site. The drug should be taken with approximately 240 mL (8 fluid ounces) of water. Additional water is allowed ad libitum except for 1 hour before and 1 hour after M3814 administration. Participants should not consume any food for at least 4 hours after the M3814 dose.

Composition of a high-fat diet: 800 to 1000 calories (protein [150 calories], carbohydrates [250 calories], fat [500 to 600 calories]). Example of high-fat diet: Two eggs fried in butter, two strips of bacon, two slices of toast with butter, four ounces of hash brown potatoes, eight ounces of whole milk

On days with scheduled PK collection visits, the morning dose should not be taken until the participant is admitted to the clinic/hospital and the morning (predose) PK collection has been completed.

If a participant misses taking a scheduled dose of M3814, it is acceptable to take the missed dose within a window of 5 hours. If more than 5 hours has passed after the scheduled dose time, the missed dose should not be taken, and the participant should be instructed to take the next dose at the next scheduled time. Any change from dosing schedule, dose interruptions, and dose reductions should be recorded in the eCRF.

On the day of avelumab administration, M3814 can be administered at any time before or after the end of avelumab infusion.

Avelumab: will be administered Q2W as an IV infusion over 1 hour, starting on Day 1, at a fixed dose of 800 mg in all dose levels. Guidance on premedication is given in Section 6.5.5.

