6.9 Management of Adverse Events of Interest

6.9.1 Adverse Drug Reactions Requiring M3814 Treatment Discontinuation or Modifications

Part A and Part FE (M3814 + Avelumab)

There is no dose reduction allowed for M3814 or avelumab during the DLT period or the FE Assessment Period. The study intervention can only be discontinued due to toxicity. Details on criteria for discontinuation of study interventions are in Section 7.1.

After the DLT and the FE Assessment Period, if not tolerated, treatment with M3814 may be interrupted, modified or stopped at the Investigator's discretion.

Where a SAE (Grade \geq 3) is believed to be due to M3814, M3814 will be withheld until the SAE has resolved to Grade \leq 2. On subsequent cases of the same SAE, permanent dose reductions in 50 mg steps must be done.

In case of a nonserious AE Grade 3, assessed by Investigators as related to M3814, a dose reduction should be considered.

In the case of participants vomits within 1 hour of M3814 dose, please see Section 6.6.5.4.

If M3814 50 mg BID is not tolerated, M3814 will be stopped. Any change from dosing schedule, dose interruptions, or dose reductions should be recorded in the eCRF.

If avelumab treatment is discontinued while M3814 treatment is ongoing, M3814 treatment could be continued if the Investigator believes the participant is experiencing clinical benefit from M3814 treatment.

Part B (M3814 + Radiotherapy + Avelumab)

The formal criteria for M3814 and RT dose modification are presented in Table 15.

Early and late toxicities related to RT and/or M3814 will be managed according to the local institute's guidelines.

Table 15 Dose Modifications for M3814 and Radiotherapy During Part B of the Study

Toxicity	Dose Modifications ^a		
	M3814 ^b	Radiotherapy ^c	
Toxicities in Radiation Field Grade ≥ 3 • Mucositis • Radiation dermatitis	Temporarily interrupt treatment. Resume treatment once severity resolves to Grade ≤ 2	Temporarily interrupt treatment. Resume treatment once severity resolves to Grade ≤ 2	
 Systemic Toxicities Hematologic Toxicities: Any Grade ≥ 4 toxicity, excluding: Grade 4 neutropenia lasting for ≤ 5 days and not associated with fever Isolated Grade 4 lymphocytopenia without clinical correlate 	Temporarily interrupt treatment. Resume treatment (at the same dose) once severity resolves to Grade ≤ 1 or Baseline. In case of a second recurrence, permanently discontinue study intervention.	No action to be taken.	

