Any PK concentrations or PK parameters excluded from summary statistics will be included in subject listings and flagged; a reason for exclusion will be detailed in the CSR (e.g. a footnote or a table of exclusions). Any flags should be included in the study specific SDTM and ADaM data sets.

The following PK parameters will be reported for M3814 and 0-demethylated product M467 (if available) on Day 1 (D1), Day 15 (D15), and Day 22 (D22) and in Part A and Part FE where data permit. Appropriate adjustments will be made for differences in molecular weight (MW) (M3814 MW = 481.92 gmol; 0-demethylated product M467 MW = 467.12 gmol). Concentration results collected on Day 22, Day 29 (Part A), and EoT will be summarized descriptively.

Cmax Maximum observed concentration.

Cmax/Dose The dose-normalized maximum observed concentration (Part A only). Normalized

using the actual dose, and the formula Cmax/Dose.

Ctrough The concentration observed immediately before next dosing on D15, D22, and D29,

(D29 is Part A only).

Ctrough/Dose The dose-normalized trough concentration. Normalized using the actual dose, and

the formula Ctrough /Dose on D15, D22, and D29, (D29 is Part A only).

AUC0-6 Area under the concentration-time curve (AUC) from time zero to time 6 hours

postdose. AUC0-6 will be based on the estimated concentration at 6 hours and not

the concentration at the actual observation time.

AUC0-6/Dose The dose-normalized AUC from time zero to 6 hours postdose (Part A only).

Normalized using the actual dose, using the formula AUC0-6/Dose.

AUC0-12 AUC from time zero to time 12 hours postdose. AUC0-12,D1 will be based on the

estimated concentration at 12 hours after dosing. AUC0-12,D15 from zero to 12 hours postdose with predose D15 concentration used for estimated concentration at

12 hours (Part A only).

AUC0-12/Dose The dose-normalized AUC0-12 (Part A only). Normalized using the actual dose,

using the formula AUC0-12/Dose.

tmax Time to reach the maximum observed concentration Cmax.

Racc(Cmax) Accumulation ratio for Cmax, calculated as Cmax,D15/Cmax,D1 (Part A only).

Frel(Cmax) Relative bioavailability of Cmax of fed (D22) compared to fasted (D15)

Cmax,fed/Cmax,fasted and Cmax of fed (D1) compared to fasted (D15) Cmax,fed/Cmax,fasted

(Part FE only).

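### The documents conflict on whether the Day 22 fed profile lies inside the FE Assessment Period, and the SAP's raw Day 22/Day 15 ratio would read unequal doses as a food effect

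*Protocol*

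**What the plan says.** **Length of the period.** Protocol 4.1.1.2 describes the FE Assessment Period of Part FE as one that "will last 3 weeks (after the first administration of study intervention) for the evaluation of the effect of food conditions (fasted/fed) on M3814 PK". Protocol 4.2 describes it as covering "single and repeated administration of M3814 over 42 doses of M3814 and 2 administrations of avelumab". Protocol 6.6.2 requires "at least 80% of the planned doses of M3814 (i.e., 34 of 42 doses with BID dosing regimen") for a participant to be evaluable for later dose-level decisions.

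**Profile days.** Protocol 6.6.5.3 sets the fed days, with breakfast served by the study centre: "On Day 1 and Day 22, participants will be instructed to fast overnight for at least 8 hours followed by the meal provided at the" … It sets the fasted day separately: "On Day 15, participants will be instructed to fast overnight for at least 8 hours followed by the M3814 administration at the site".

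**Dose changes.** Protocol 6.9.1 bars M3814 reductions during the DLT period or the FE Assessment Period, then continues: "After the DLT and the FE Assessment Period, if not tolerated, treatment with M3814 may be interrupted, modified or stopped". That decision is left to the investigator. Reductions go in 50 mg steps.

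**Text pointing the other way.** The Table 4 header for Part FE places Visits 1 to 3, the third being Day 22, under a DLT Period label. Protocol 6.6.2 treats the period as completed "when the PK and minimum safety evaluations have been performed (hematology, chemistry, and clinical assessments), and the participant has received" the required doses.

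**Analysis.** SAP 16.1 defines relative bioavailability in Part FE as Day 22 over Day 15, for Cmax and for AUC0-6. Day 1 over Day 15 is a second comparison, labelled a sensitivity analysis for AUC0-6. Neither formula contains the dose. Cmax/Dose is described as "The dose-normalized maximum observed concentration (Part A only"), and AUC0-6/Dose carries the same restriction.

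**The concern.** The fed arm of the main food-effect ratio is measured on Day 22. If the period set up to measure it closes the evening before, the bar on dose reductions has lapsed when the fed profile is taken. A participant could then have a fasted profile at one dose and a fed profile at a lower one, fully within the protocol. The SAP would divide one by the other without adjustment.

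That ratio carries the Part FE primary comparison, and Protocol 6.6.2 says that the Part FE results may affect the M3814 dosing recommendations. Cohorts are 3 to 6 participants, so one such pair carries weight. Day 22 is also the first visit after Day 1 at which Table 4 schedules haematology, chemistry and a complete physical examination, so it is a plausible point for a dose decision.

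**Working it through.** **1. The protocol's own count.** 21 days × 2 doses = 42. The threshold is 0.8 × 42 = 33.6, rounded up to 34. Both figures agree with the protocol, so the 42 doses are those of Days 1 to 21.

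**2. Where the profiles fall.** The morning dose on day d is number 2(d − 1) + 1.

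- Day 15 (fasted): 2 × 14 + 1 = 29, inside.
- Day 22 (fed): 2 × 21 + 1 = 43, the first dose after the 42.
- Day 15 morning to Day 21 evening: doses 29 to 42, i.e. 14 doses, all inside.

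**3. Effect of the ±1 day visit window in Table 4.**

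| Visit held on | Fed profile dose | Inside the 42? | Earlier doses already outside |
|---|---|---|---|
| Day 21 | 41 | yes | 0 |
| Day 22 | 43 | no | 0 |
| Day 23 | 45 | no | 2 (doses 43 and 44) |

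On this count the opening is the profile dose itself, plus at most two doses before it.

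**4. Whether the analysis would catch it.** The Part FE PK Analysis Set (SAP 8.2) needs one administration of M3814 and avelumab from Day 1 and one measurable postdose sample; it does not require equal doses on the compared days. SAP 16.1 allows exclusion for protocol violations and for processing or analytical errors, and keeps other implausible concentrations. A reduction that 6.9.1 permits is none of these, so the pair stays in.

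**5. Size.** Inputs: 100 mg and 200 mg twice daily (Protocol Table 12), one 50 mg step (6.9.1, taken as applying to each dose), and n of 3 or 6 per dose level (6.6.2). The geometric mean is among the summary statistics in SAP 9.2.2. With one affected participant and every other ratio equal to 1, the geometric mean ratio is (Day 22 dose / Day 15 dose)^(1/n).

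| Change | Individual ratio | n = 3 | n = 6 |
|---|---|---|---|
| 100 to 50 mg | 0.50 | 0.794 | 0.891 |
| 200 to 150 mg | 0.75 | 0.909 | 0.953 |

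Under the same assumptions the ratio returns to 1.00 if it is dose-normalised or the pair is excluded.

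**The case against.** The strongest reply is that Day 22 is inside the period. Three weeks after a first dose on Day 1 can be counted as Day 22, the Table 4 header groups Day 22 with the protected visits, and 6.6.2 makes completed PK evaluations a condition of completion. This is a fair reading, which is why the point is a conflict and not a settled gap. It is not decisive. Protocol 4.1.1.2 defines a DLT period only for Parts A and B, and SAP 8.2 sets that of Part A at 21 days. Section 6.6.2 names no PK day and repeats the three weeks. The sentence in 6.6.5.4 ruling out toxicity reductions within a participant follows text on avelumab, whereas 6.9.1 expressly provides for M3814 reductions.

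It can also be said that an affected pair would be seen. SAP 16.1 lists parameters by dose and day, plots the pairs, and pre-specifies Day 1 against Day 15. That stands as mitigation, but Day 1 against Day 15 compares a first dose with repeated dosing, and the summarised ratio would still be wrong. SAP 16.1 says generally that parameters use the actual administered dose, but the ratio's formula has no dose term.

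Four stronger readings are tempting, and the documents do not support them:

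- *The dose may change at any time between the two profiles.* Doses 29 to 42 all fall where reductions are barred.
- *Missed doses just before Day 22 escape the rules.* With the visit on Day 22 they fall within the 42 and count towards compliance and the 34-dose threshold. They are a separate matter, which dose-normalisation does not correct.
- *No dose-normalised parameter applies to Part FE.* Ctrough/Dose is defined for Days 15 and 22 and confined to Part A only on Day 29. The restriction that matters here is on Cmax and AUC0-6.
- *The food effect will be off by about 20%.* The 0.79 is the most severe of the four cases shown.

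**Conclusion.** The point holds in limited form. The protocol does not say consistently whether the Day 22 fed profile is inside the FE Assessment Period. On the 42-dose reading it is the first dose outside, dose modification is open from that dose, and SAP 16.1 would report a permitted dose difference as a food effect.

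The cohort ratio would move to between 0.79 and 0.95 for one affected participant. This assumes dose proportionality (not stated in the documents), no true food effect and negligible carry-over from earlier full doses; carry-over would bring the individual ratio closer to 1. The documents give no basis for saying how often such a change would occur. The study is exploratory and tests no hypothesis, so no power or sample-size figure is affected. It merits correction before database lock because it touches a primary comparison and costs little.

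**What to change.** **Protocol.** Reconcile 4.1.1.2, 6.6.2, 6.9.1 and Table 4 so that they state the same thing about whether the Day 22 profile is inside the FE Assessment Period. Which dose-modification rule then applies on Day 22 is for the sponsor to decide.

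**SAP 16.1.** Whatever that answer, state how unequal doses are handled. Either compute relative bioavailability from Cmax and AUC0-6 divided by the actual dose on each day, or exclude from its summary any pair whose compared doses differ. List those pairs in both cases. Normalisation keeps the participant but relies on dose proportionality and negligible carry-over, which the predose samples can help to judge. Exclusion needs neither assumption but costs a participant in a cohort as small as 3. Missed doses before Day 22 need their own rule or listing.

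**Cost.** Wording in both documents and one change to a derivation; no added samples, visits or participants.

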4.1.1.3 Follow-Up Periods

Safety Follow-up

Part A, Part B, and Part FE

The Safety Follow-up period will be 30 days and 90 days after the last dose of avelumab for safety evaluation of the combination of study interventions.

Part B

In addition to the Safety Follow-up relating to the combination of study interventions after the last dose of avelumab, for Part B, the following RT Safety Follow-up periods are defined to assess potential toxicity of RT when administered in combination with M3814 and avelumab:

- Short-term RT Safety Follow-up: 30 days after the end of RT for evaluation of safety.
- Mid-term RT Safety Follow-up: 3 months after the end of RT to evaluate late signs of RT-induced toxicity on normal surrounding tissues.
- Long-term RT Safety Follow-up: 12 months after the end of RT, to evaluate RT-induced toxicities, by telephone call.

Long-Term Follow-up

Part A, Part B, and Part FE

Participants will be followed for survival and use of subsequent anticancer therapy until the end of the study. Participants without PD who are not receiving subsequent anticancer therapy after the End of Treatment Visit, will be followed every 8 weeks with radiographic disease evaluation for the first 6 months of the study and then every 12 weeks thereafter until PD according to Response Evaluation Criteria in Solid Tumors Version 1.1 (RECIST v 1.1), and for survival and use of subsequent anticancer therapy until the end of the study.

